12.5. Subject Confidentiality

The investigator must ensure the anonymity of each subject is maintained at all times. Subjects should only be identified by their initials and Subject Trial ID (enrolment) number on the CRF, or on any other trial documents provided to the Sponsor or their designate(s). Any documents that identify the subject should be kept in strict confidence by the principal investigator.

Based on ICH GCP guidelines and regulatory requirements, the investigator is required to allow authorized personnel of Medexus (or its designate), the IRB/EC, and members of the appropriate regulatory authorities to review subject's files that are related to APVO101-903. Subjects and/or their parent or legal guardian must be informed that his/her records may be reviewed by Medexus, its designate(s), the IRB/EC and the appropriate regulatory authorities through direct access to the subject's original medical records.

13.2. Protocol Amendments

Protocol amendments will only be made by Medexus. Any change to the protocol must be made in the form of a formal amendment to the protocol and must be approved in writing by the principal investigator, the sponsor, and the IRB/EC and regulatory agencies (where applicable) prior to implementation. The investigator must receive written IRB/EC approval for all protocol amendments prior to implementing protocol amendments at the trial site, and the investigator must send a copy of any IRB/EC correspondence and all approval/disapproval letters from the IRB/EC to Medexus.

13.3. Deviations from the Protocol

The investigator agrees to conduct the clinical trial in compliance with the protocol agreed to by Medexus and approved by the IRB/EC. The investigator and Medexus shall sign the protocol to confirm this agreement.

The investigator will not deviate from this protocol for any reason without prior approval of the sponsor and the IRB/EC, except in cases of medical emergencies. The investigator may deviate from the protocol without the prior approval of the IRB/EC or Medexus only when the deviation is necessary to eliminate an apparent immediate hazard to the subjects. In that event, the investigator must notify the IRB/EC and Medexus in writing as soon as possible and no more than five working days after the deviation is implemented. The investigator shall document and explain any deviation from the approved protocol.

13.4. Source Documentation and Storage

The principal investigator will maintain the following information:

- Medical history/physical condition of the trial subject before involvement in the trial sufficient to verify protocol entry criteria.

- Dated and signed notes on the day of entry into the trial including the trial number, the drug being evaluated, subject trial ID number assigned, and a statement that informed consent/assent form was obtained, noting the time the consent was obtained.
- Dated and signed notes from each trial subject visit that refer to the protocol or CRFs for further information, if appropriate (i.e., for specific procedures and exams).
- Subject diary page(s) following the assessment visit.
- The investigator will assess each abnormal lab result as clinically significant or not clinically significant. For clinically significant results, a brief explanation will be written on the laboratory report. These assessments will be noted on the laboratory report source document and signed and dated on the date of the investigator's review.
- Notes regarding concomitant medications taken during the trial (including start and stop dates).
- Source documents regarding adverse events occurring during the trial including date of onset and cessation, seriousness, severity, causality, action taken and related concomitant medications.
- Trial subjects' condition upon completion, or withdrawal from, the trial.
- All communications with the IRB/EC responsible for the trial.
- Drug accountability records.
- Any other records as required by the Sponsor/designate, the IRB/EC or the regulatory authorities.

The investigator must arrange for the retention of the subject identification codes according to local regulatory requirements. Subject files and other source data must be securely stored and kept for the maximum time permitted by the hospital, institution or private practice but not less than local regulatory requirements. Archival data may be held on microfiche or electronic record, provided that a backup exists, and that hard copy can be obtained from it if required. If source documents are to be destroyed as per hospital or local regulatory policy, the investigator is requested to contact the sponsor.

Records from the trial that identify the subject will be confidential except that they may be given to and inspected by the sponsor of the trial or designate(s), the IRB/EC, the Food and Drug Administration, other government agencies as appropriate, and will not otherwise be released except as required by law. All information provided to the investigator by the sponsor is to be considered confidential unless otherwise stated.

13.5. Data Forms

Detailed specifications for data management will be outlined in a Data Management Plan (DMP) that will be finalized before data collection is initiated. The DMP is a dynamic document that will be updated throughout the conduct of the study, as needed, to ensure the accuracy and quality of the database.

Designated study site personnel will record study data into electronic CRFs within the study electronic data capture (EDC) system. The investigator is responsible for the accuracy of the data entered into the CRFs and will be required to electronically sign the forms to indicate agreement with the recorded data.

Security processes will be in place to ensure the safety of all systems and data. Every effort will be made to ensure that data are kept secure so that they can only be accessed by authorized staff.

13.6. Monitoring

At the time the trial is initiated, monitors from the sponsor/CRO will thoroughly review the protocol and data forms with the investigators and their staff. During the trial, the monitors will be available to discuss by telephone, e-mail, or in person (during site visits), questions regarding study criteria, adverse reactions, removal of subjects from the trial, conduct of the trial and other clinical trial matters. Monitors from the sponsor/CRO will visit at the initiation of the trial, during the trial and at the completion of the trial. At the time of each monitoring visit, the monitors will check the case report forms of the subjects to ensure that all items have been completed, that the data are accurate and obtained in the manner specified in the protocol and that data recorded on the data forms for the trial agree with medical records at the site. The monitors will also check for general protocol and regulatory compliance by subjects and site personnel.

13.7. Quality Control and Quality Assurance

Medexus Quality Assurance department (or authorized representatives) may conduct onsite audits of all aspects of the clinical trial prior to, during the trial, or after the trial has been completed. The clinical trial may also be inspected by regulatory authorities or the IRB/EC to verify that the trial is being or has been conducted in accordance with protocol requirements, GCP, as well as the applicable regulatory requirements.

13.8. Publication Policy

Data arising from this trial are the sole property of the sponsor of the trial, Medexus. The sponsor must provide written, prior agreement to any publication based, in whole or in part, on data from this trial. All proposed abstracts, manuscripts or presentations from the study must be provided to Medexus for review at least 60 days prior to submission for publication/presentation. Any information identified by Medexus as confidential must be deleted prior to submission.

The Publication Policy applicable to this protocol is the one agreed upon and described in the Clinical Trial Agreement between Medexus and the principal investigator.

1. LIST OF ABBREVIATIONS

ABR	Annualized bleed rate
AE	Adverse event
ALP	Alkaline Phosphatase
ALT	Alanine Aminotransferase
AST	Aspartate Aminotransferase
ATC	Anatomical Therapeutic Chemical
bp	Base pairs
bpm	Beats per minute
BUN	Blood Urea Nitrogen
CBC	Complete Blood Counts
CHOP	Chinese hamster ovary cell proteins
eCRF	Electronic case report form
ED	Exposure day
F1+2	Fragment 1+2
IV	Intravenous
MedDRA	Medical Dictionary for Regulatory Activities
PK	Pharmacokinetics
PT	Preferred Term
SAE	Serious adverse event
SAP	Statistical analysis plan
SOC	System Organ Class
SMC	Safety Monitoring Committee
SD	Standard Deviations
TAT	Thrombin-antithrombin complex
TEAE	Treatment Emergent Adverse Event
Q1/Q3	Quartile 1/Quartile 3

2. DEFINITIONS

Annualized Bleeding Rate (ABR) is defined as number of bleeding episodes per year.

An adverse event (AE) is defined as any untoward, undesirable, or unintended medical occurrence in a clinical trial subject administered APVO101 which does not necessarily have a causal relationship with APVO101. For purposes of this clinical trial, an AE can therefore be any unfavorable and unintended sign (e.g., including an abnormal laboratory finding), symptom, or disease temporally associated with the use of APVO101, whether or not related to the product.

Examples of **major surgical procedures** (surgery) include synovectomy, knee or hip replacement, total tooth extraction, tonsillectomy and/or adenoidectomy, surgery for intracranial hemorrhage, radial head excision, arthrodesis, ankle surgery, abdominal surgery, herniorrhaphy, or surgery for major muscle bleed management.

A **bleeding episode** will be defined as a unique entry in the subject bleeding diary. In the event that a bleeding episode occurring at multiple locations is recorded as multiple entries in the bleeding diary, these will be considered as one bleeding episode provided that all entries have the same start date.

Bleeding episodes severity:

- Minor: e.g., uncomplicated hemarthroses and superficial muscle (except iliopsoas) with no neurovascular compromise, other soft tissue bleeds
- Moderate: e.g., hemarthrosis of longer duration, recurrent hemarthrosis, mucous membranes, deep lacerations, hematuria
- Major or life-threatening: e.g., iliopsoas, deep muscle with neurovascular injury, substantial blood loss, central nervous system, pharyngeal, retropharyngeal, retroperitoneal.

Compliance will be calculated for each subject based on actual and planned number of APVO101 doses in the study. The actual number of doses will be counted from the first dose in the treatment phase up to and including the last APVO101 dose date on study. The number of infusions expected will be calculated for each subject based on their prescribed dosing regimen. If a patient received APVO101 dose twice weekly during whole study compliance will be calculated as following:

Compliance % = $100\% * [\text{number of infusions recorded in the subject diary} / (\text{date of last dose for prophylaxis} - \text{date of first dose}) * 2/7]$

if a patient first received APVO dose twice weekly and then dose frequency was adjusted to once weekly per investigator discretion, compliance will be calculated as following:

Compliance % = $100\% [\text{number of infusions recorded in the subject diary} / (A + B)]$, where $A = [2 * (\text{date of last dose when patient was on 'twice weekly' frequency} - \text{date of first dose})] / 7$

$B = (\text{date of last dose when patient was on 'once weekly' frequency} - \text{date of first dose when patient was on 'once weekly' frequency}) / 7$

If patient dose-frequency was changed more than once, compliance will be calculated similar to the above but taking into account all periods of different dose frequencies in the denominator.

The following **measures of exposure** will be presented for the study:

Parameter	Description
Exposure Day (ED)	APVO101 exposure/infusion. ED will be calculated as the total number of APVO101 infusions during all phases of the study: Pharmacokinetic (PK) [1], Treatment, and Continuation phases, including surgery if applicable. If a subject receives more than one infusion in a single day, all infusions on that day will count as one ED.
Average Exposure per exposure day (IU)	Average APVO101 dose (IU): Sum of all dosages received by a subject (excluding PK doses and dosing during surgery), divided by number of exposure days (excluding PK and surgery)
Average Exposure per exposure day (IU/kg)	Similar to above but for dose in IU/kg
Total Exposure (IU) – PK phase	Planned PK dose IU [2]
Total Exposure (IU/kg) – PK phase	Planned PK dose IU/kg [2]
Total Exposure (IU) –	N/A, no surgeries in the study at the moment of the Statistical Analysis

Surgeries	Plan (SAP) update [3]
Total Exposure (IU/kg) – Surgeries	N/A, no surgeries in the study at the moment of the SAP update [3]
Total Exposure (IU) – All Phases combined including surgeries	Sum of all doses (IU) during the study (PK [1], Treatment and Continuation phases, including surgery if applicable).
Total Exposure (IU/kg) – All Phases combined including surgeries	Similar above but for dose in (IU/kg)

[1] including additional PK during Treatment/Continuation phases

[2] PK during Treatment/Continuation phases should not be included

[3] if surgeries occur in the study by the time of database lock, exposure during surgeries will be derived similar to other total exposure parameters, i.e., as sum of all doses in IU or IU/kg associated with surgery.

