8. ASSESSMENT OF APVO101 EFFICACY

8.1. Subject's Assessment of Efficacy

Throughout the study, subjects and/or their parent or legal guardian will maintain a subject diary to record information about each APVO101 infusion, any AEs and all bleeding episodes (trauma or spontaneous). An assessment of efficacy will be made for each bleeding episode. In the event of trauma, details will be recorded.

Within 6 hours (exact time to be recorded) after the subject believes the bleeding has stopped, an overall evaluation of efficacy of treatment will be provided. This will be done using the following verbal descriptors:

- Excellent: a dramatic response with abrupt pain relief and clear reduction in joint or hemorrhage site size
- Good: pain relief or reduction in hemorrhage site size that may have required an additional infusion for resolution
- Fair: probable or slight beneficial response usually requiring one or more additional infusions for resolution
- Poor: no improvement or condition worsens

In addition to the description of efficacy, the subject and/or their parent or legal guardian will indicate the following:

- How long it took the bleeding to stop
- How long it took the pain to stop
- How long it took the swelling (if present) to resolve

This will be done for each variable using a series of check boxes for time intervals ranging from < 2 hours to 72+ hours after the onset of the bleeding episode.

The study investigator will be contacted by the subject, if efficacy of two consecutive APVO101 infusions is rated as 'fair' or 'poor'. The subject will be instructed to call the treatment center if there is an occurrence of 'poor' or no response to the therapy (i.e., sub-optimal response; see [Section 8.2](#)) for a specific bleeding episode.

The subjects and/or their parent or legal guardian will document in the diary if no bleeding episodes occurred.

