10.7.1 ANALYSIS OF PRIMARY EFFICACY ENDPOINT

The number of bleeding episodes and the number of months observed will be determined from the subject diary. The months of observation will be calculated from the first date of the Treatment Phase to the last prophylaxis entry into the subject diary.

ABR while on prophylaxis to prevent bleeding episodes will be calculated and summarized using median, Q1, Q3 and 95% exact confidence interval for the mean, assuming that the rates follow a Poisson distribution.

ABR overall = (number of bleeding episodes starting from first dose after PK Phase up to 3 days after the last dose of APVO101 given for prophylaxis)/[(treatment end date +3 – treatment start date+1)/365.25]. If a subject left the study earlier than 3 days after last dose, date of end of study will be taken instead of (treatment end date +3 days).

ABR Treatment Phase = (number of bleeding episodes starting from first dose after PK Phase up to 3 days after the last dose of APVO101 given for prophylaxis up to 50 ED)/[(last dose ≤50ED +3 – treatment start date +1)/365.25]. In case first dose after 50 ED occurred earlier than 3 days after 50 ED then this dose date – 1 should be taken as reference end date. If a subject left the study earlier than 3 days after last dose in treatment phase, date of end of study will be taken instead of (last dose ≤50 ED + 3 days).

ABR Continuation Phase = (number of bleeding episodes starting from first dose after 50 ED up to 3 days after last dose of APVO101 given for prophylaxis)/[(treatment end date +3 – first dose after 50 ED+1)/365.25]. If a subject left the study earlier than 3 days after last dose, date of end of study will be taken instead of (treatment end date +3 days).

Note: a bleeding episode which occurred after PK dose but prior to completion of PK assessment will be included into ABR calculations.

In addition, analysis of ABR will be repeated on the normalized data (square-root transformation will be used to normalize ABR).

Number of subjects with at least one bleeding episode and no bleeding episodes will also be summarized.

The analysis of ABR will be repeated for Spontaneous ABR which will consider only spontaneous bleeding episodes in the numerator. Denominator will remain the same as for ABR. Spontaneous ABR for Treatment, Continuation phases as well as overall will be derived.

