10.7.2 ANALYSIS OF SECONDARY EFFICACY ENDPOINTS

Both types of secondary efficacy endpoints (bleeding episode level and subject level) will be presented descriptively for the Treatment Phase (bleeding episodes and subject level assessments occurred from first dose to 50 ED up to 3 days after last dose of APVO101 given for prophylaxis), Continuation Phase (bleeding episodes and subject level assessments occurred on or after first dose after 50 ED given for prophylaxis) and overall (all bleeding episodes and subject level assessments in a subject).

Summaries for bleeding episode level endpoints will include:

- Number and percentage of bleeding episodes within each category of subject's rating of efficacy;
- Number and percentage of bleeding episodes within each category reported by subjects as answer to question "How long did it take for the pain to stop?"
- Number and percentage of bleeding episodes within each category of highest level of pain during the bleeding episode.
- Number and percentage of bleeding episodes within each category reported by subjects as answer to question "How long did it take for the swelling to go down?"
- Descriptive statistics for time from onset of bleeding to the first infusion (minutes) as continuous variable

- Descriptive statistics for time from onset of treatment until resolution of the bleeding episode (minutes) as continuous variable
- Descriptive statistics for number of infusions required to treat the bleeding episode as continuous and categorical variable

Note: a bleeding episode which occurred after PK dose but prior to completion of PK assessment will be included into ABR calculations.

Summaries for subject level endpoints will include by-visit summaries for the following Investigator's assessments:

- APVO101 prophylaxis efficacy assessment
- Efficacy for control of bleeding episodes assessment

All data for subject assessments of bleeding episodes and Investigator assessments of efficacy will be listed.

10.7.3 ANALYSIS OF EXPLORATORY EFFICACY ENDPOINTS:

The following endpoints related to surgery will be summarized as frequency variables:

- Pre- and Post-surgery assessments:
 - Surgeon's assessment of total blood loss
- 12 hours (± 3 hours) post-surgery assessment and 24 hours (± 3 hours) post-surgery assessment:
 - Surgeon's assessment of total blood loss
 - Surgeon's assessment of APVO101 hemostatic efficacy

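### The SAP counts every diary entry as a bleed and has no rule for a same-site bleed re-entered on a later date while still under treatment, so one slow bleed can count as several

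*SAP*

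**What the plan says.** SAP section 2 builds the primary endpoint on episodes: "Annualized Bleeding Rate (ABR) is defined as number of bleeding episodes per year". A bleeding episode in turn "will be defined as a unique entry in the subject bleeding diary". There is one exception, for a single bleed at several sites that the family has entered more than once: "these will be considered as one bleeding episode provided that all entries have the same start date".

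The same count is then used in several places:

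- SAP 10.7.1, primary endpoint: "The number of bleeding episodes and the number of months observed will be determined from the subject diary".
- SAP 10.7.1, spontaneous ABR, which keeps "only spontaneous bleeding episodes in the numerator" over the same denominator.
- SAP 10.7.2, secondary endpoints: "Descriptive statistics for number of infusions required to treat the bleeding episode as continuous and categorical variable".
- SAP 10.8.4.2, which tabulates location, cause and side by episode.

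The protocol does not define a bleeding episode. Protocol 8.1 has families time the resolution of each bleed in boxes for "time intervals ranging from < 2 hours to 72+ hours after the onset of the bleeding episode", and its Good and Fair ratings both allow for further infusions.

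**The concern.** The protocol foresees bleeds that run over several calendar days and need more than one infusion. Suppose a knee bleed is infused on Monday and the parent opens a new entry on Tuesday because it still hurts and is infused again. The second entry has a different start date and a single location, so the combining sentence does not reach it. The SAP then counts two bleeds with one infusion each instead of one bleed with two. A second same-day entry for the same joint would also stay separate, because the sentence deals only with multiple locations.

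The effect on the two efficacy questions runs in opposite directions: prevention looks worse (higher ABR) and control looks better (fewer infusions per bleed). Both questions belong to a primary objective. Expected counts are low, so a few such entries can matter.

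A second, smaller gap concerns cause. If several entries are merged as one multi-location bleed and their recorded causes differ, the SAP does not say whether the merged episode is spontaneous, although spontaneous ABR and the table of causes both need that answer.

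**Working it through.** The plan gives no target ABR and no sample size calculation (Protocol 11.1), so there is no figure of its own to reproduce. The check applies the SAP 10.7.1 formula with and without one extra entry.

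**Inputs**

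- Treatment Phase ABR = bleeds / [(last dose at or before 50 ED + 3 − treatment start + 1) / 365.25] (SAP 10.7.1).
- Twice-weekly infusions, so 3.5 days apart, to 50 ED (Protocol 5.7.1). Infusions given for bleeds are ignored when setting the phase length.
- 20 children, the top of the 15 to 20 evaluable range (Protocol 11.1).
- Participation expected to last at least 12 months (Protocol 3.1).
- For scale, previous median ABRs on prophylaxis of 0.3 (pediatric study) and 1.52 (mainly adolescents and adults) (Protocol 1.2.2). These are medians, used here as if they were mean rates.

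**Phase length**

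- PK dose counted as an ED, as in SAP section 2: 49 infusions follow, so 48 × 3.5 + 3 + 1 = 172 days.
- PK dose not counted: 49 × 3.5 + 3 + 1 = 175.5 days.

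**One extra entry**

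- One child, Treatment Phase: 365.25 / 172 = 2.12, or 365.25 / 175.5 = 2.08.
- Mean of 20 children: 2.12 / 20 = 0.106, or 2.08 / 20 = 0.104.
- Over one year: 1 for the child and 1 / 20 = 0.05 for the mean.

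**One bleed infused on three dates (172 days, phase length held fixed)**

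- Entered once: ABR 2.12, with 3 infusions per bleed.
- Entered three times: ABR 3 × 2.12 = 6.37, with 1 infusion per bleed.

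**Group mean with exact Poisson 95% interval, 20 children**

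Person-years in the Treatment Phase are 20 × 172 / 365.25 = 9.42.

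| Setting | Bleeds | Mean ABR (95% CI) | With one split bleed |
|---|---|---|---|
| Treatment Phase, rate near 0.3 | 3 | 0.32 (0.07 to 0.93) | 0.42 (0.12 to 1.09) |
| Treatment Phase, rate near 1.52 | 14 | 1.49 (0.81 to 2.49) | 1.59 (0.89 to 2.63) |
| One year, rate 0.3 | 6 | 0.30 (0.11 to 0.65) | 0.35 (0.14 to 0.72) |

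The relative rise is 1/3 = 33%, 1/14 = 7% and 1/6 = 17%.

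**General form.** If extra entries amount to a fraction f of true bleeds, ABR is multiplied by 1 + f and mean infusions per bleed by 1 / (1 + f). For f = 10%, 20% and 30% this gives 1.10, 1.20 and 1.30 for ABR, and 0.91, 0.83 and 0.77 for infusions per bleed. These fractions are assumptions; the documents give none.

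**The case against.** The diary is designed to hold a slow bleed in one record. Protocol 10.2 has the family record, for each bleed, the doses given and the outcome. Protocol 8.1 asks for one overall rating once the bleeding is thought to have stopped. On this view the open-ended last time box shows that one record can span days, not that families will open a second. Families are trained at Screening (Protocol 6.1), the diary is reviewed with them at each visit (Protocol 5.7.3), and they contact the investigator after two consecutive infusions rated fair or poor (Protocol 8.1). All data are listed (SAP 10.1, 10.7.2), so with at most 22 children repeat entries could be found by eye. All analyses are descriptive.

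Most of this stands, and it makes re-entry less likely. But none of these steps tells a site or a programmer when two entries are one bleed. The listings would show the entries, while the summary tables would simply count them.

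A reader might go further and infer that the combining sentence makes unrelated same-day bleeds count as one, so that a traumatic lip bleed in the morning and a spontaneous elbow bleed that evening would merge and flatter prevention. The text does not support that. The sentence applies only to one bleed at multiple locations, and the shared start date is a further condition on that case, not an instruction to merge whatever starts on the same day. What remains is that start date is the only test stated for applying the sentence, and that the class of a mixed-cause merger is undefined.

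**Conclusion.** The gap is real and should be closed before database lock. As written, a same-site bleed re-entered on a later date counts again, raising ABR and lowering infusions per bleed. One such entry is worth about 2.1 on that child's Treatment Phase ABR and about 0.10 on a 20-child mean, or about 1 and 0.05 over a year. These figures rest on twice-weekly dosing and equal follow-up.

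Three limits apply. The documents give no frequency for re-entry, so this is a possible distortion and not a demonstrated bias in the result. Splitting cannot turn a bleed-free child into one with bleeds, so that count is safe. No hypothesis test is planned, so no error rate is affected; the exposed quantities are the ABR summaries, above all the mean to which the exact interval is attached, and the per-bleed summaries.

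The cause question is a smaller matter of wording and does not amount to an order to merge unrelated bleeds.

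**What to change.** Amend SAP section 2 as follows.

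1. Combine entries at the same location and side, with no new recorded cause (for example a new trauma), when the later one starts within a pre-specified window of the last infusion given for the earlier entry. Date the episode from the first entry and sum the infusions. A window of 72 hours would serve, but as an analysis choice: the diary's last box is open-ended and runs from onset, so it does not supply the figure.
2. State that same-day entries at multiple locations merge only when they share the same recorded cause. Entries with different causes stay separate, each with its own spontaneous or traumatic class.
3. Report ABR, spontaneous ABR and infusions per bleed under both this rule and the current entry count. The documents do not state which bleed rule the previous studies used, so the entry-count line should not be presented as matching them unless that is confirmed.

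The cost is slightly more programming and a second ABR line. Location, side and cause are already to be tabulated (SAP 10.8.4.2), and the date and time of each dose and the doses used for each bleed are already recorded in the diary (Protocol 10.2). Nothing changes for the children or the sites.

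### The SAP compliance formula sets all diary infusions against expected prophylaxis infusions only, so extra bleed doses can offset missed prophylaxis and full adherence scores about 101–103%

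*SAP*

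**What the plan says.** SAP section 2 defines compliance per subject, "based on actual and planned number of APVO101 doses in the study". Actual doses run from the first Treatment Phase dose "up to and including the last APVO101 dose date on study". Expected infusions come from the prescribed regimen.

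- **Twice weekly throughout.** The numerator is the "number of infusions recorded in the subject diary". The denominator is the time from the first dose to the "date of last dose for prophylaxis", converted at 2 infusions per 7 days.
- **Twice weekly, then once weekly.** The numerator is the same and the denominator is A + B. A covers the first to the last twice-weekly dose, and B the first to the last once-weekly dose.
- **More than one change.** The same approach applies, "taking into account all periods of different dose frequencies in the denominator".

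Protocol 8.1 states that subjects or their parents "will maintain a subject diary to record information about each APVO101 infusion". Protocol 10.2 adds that the doses needed for each bleed are recorded. SAP 10.8.1 reports compliance for the whole study, as a continuous variable and split at 80%.

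**The concern.** The two parts of the ratio count different things. The numerator takes in every diary infusion, whatever its purpose, up to the last dose of any kind. The denominator holds scheduled prophylaxis only and, in the twice-weekly formula, stops at the last prophylaxis dose. Nothing in the compliance text removes bleed-treatment infusions. The same section does separate dose types for average exposure, "excluding PK doses and dosing during surgery", so a restriction was written where one was wanted.

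A second fault has nothing to do with bleeds: elapsed time divided by the dosing interval gives the number of intervals, which is one fewer than the number of doses. At a frequency change, the interval between the last twice-weekly and the first once-weekly dose is in neither A nor B.

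At stake is the compliance table, above all its 80% split. SAP 10.1 summarizes data by age group, and Protocol 3.3 targets 10 subjects in each, so one child on the wrong side of the cut moves a group's proportion by 1/10 = 10 points. The bleed component is also largest for the children who bleed most.

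**Working it through.** The plan states no compliance figure, so there is none to reproduce. The check evaluates the formula as intended, with the twice-weekly denominator read as (last − first) × 2/7, the form that term A takes.

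**Inputs**
- Twice-weekly schedule (SAP 5.1.2): 365.25 × 2/7 = 104.36 planned infusions a year.
- ABR on prophylaxis in the earlier pediatric study (Protocol 1.2.2): median 0.3, maximum 1.6.
- Cut at 80% (SAP 10.8.1).
- Infusions per bleed: 1 to 3. This is an assumption; the documents give no figure.

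**1. Full adherence, no bleeds.** N evenly spaced doses span N − 1 intervals, so the score is N/(N − 1).
- 50 doses: 50/49 = 102.0%.
- 104 doses: 104/103 = 101.0%.
- On calendar dates with alternating 3- and 4-day gaps, 50 doses span 171 or 172 days. Expected: 171 × 2/7 = 48.86 or 172 × 2/7 = 49.14. Scores: 102.3% or 101.7%.

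**2. Full adherence with a frequency change.** Take 52 twice-weekly doses, then 26 once-weekly doses. A = 51 and B = 25, so the score is 78/76 = 102.6%. Restoring the lost interval gives 78/77 = 101.3%; the rest is the missing first dose.

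**3. Average effect of bleed infusions.** Added points = 100 × ABR × infusions per bleed × share additional to schedule / 104.36.

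| Share additional | ABR 0.3, 1 to 3 infusions | ABR 1.6, 1 to 3 infusions |
|---|---|---|
| All | 0.3 to 0.9 | 1.5 to 4.6 |
| Half | 0.1 to 0.4 | 0.8 to 2.3 |
| None (all replace scheduled doses) | 0 | 0 |

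For example, 100 × 1.6 × 3 / 104.36 = 4.6.

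**4. The 80% cut, over 104 planned doses.** The SAP denominator is 103, so showing at least 80% takes 0.8 × 103 = 82.4, that is 83 recorded infusions.
- No bleeds: only a subject with 83 doses changes category (83/104 = 79.8% true, 83/103 = 80.6% shown). With 82 doses the score is 82/103 = 79.6%, below the cut either way.
- One bleed with 3 additional infusions: 80 scheduled doses (80/104 = 76.9%) show as (80 + 3)/103 = 80.6%.

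**5. On-demand time.** Protocol 5.7.3 foresees a change to on-demand treatment; the compliance text has no rule for it. After the last prophylaxis dose, on-demand infusions add to the numerator and nothing to the denominator, so the score rises. Between two prophylaxis periods, the twice-weekly denominator keeps accruing expected doses, which pushes the score down.

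**6. The amended formula (see fix).**
- Step 2 example: 182 × 2/7 + 175/7 + 1 = 78, and 78/78 = 100%.
- Step 4 example: 80/(360.5 × 2/7 + 1) = 80/104 = 76.9%.
- 50 doses on calendar dates: 50/49.86 = 100.3% or 50/50.14 = 99.7%.

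**The case against.** The best defence is that the SAP may not mean what it literally says. It compares actual with planned doses under the prescribed regimen, it refers elsewhere in section 2 to a bleeding diary, and SAP 10.7.1 speaks of a prophylaxis entry in the diary. The eCRF or the table shells could therefore confine the count to prophylaxis records. That stands as a possibility. Against it, Protocol 8.1 describes one diary for infusions and bleeds, and the SAP text extends the count to the last dose of any kind.

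It is also fair to say that the effect is small. Without bleeds, one dose count in the 104-dose example changes category, and at the earlier median ABR the average addition is under 1 point. That stands too.

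Four stronger readings are tempting, and the documents do not support them:
- A reader might apply the 4.6-point average to one child and infer that true compliance near 75% could show as 80%. An ABR of 1.6 over 360.5 days is 1.6 × 360.5/365.25 = 1.58 bleeds. A single child within that rate has at most one whole bleed, and with 3 additional infusions the lowest true value is 76.9%.
- A reader might infer that the error is always upward. Step 5 shows otherwise for on-demand time inside the window.
- A reader might take the twice-weekly formula strictly left to right and find a score near 8% at full adherence. Term A shows the intended form, and the bracket may have been lost in text extraction, so this carries no weight.
- A reader might infer damage to the efficacy results. Compliance enters neither the ABR formulas (SAP 10.7.1) nor the population definitions (SAP 9).

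**Conclusion.** The concern holds as a minor error in the formula as written. Bleed infusions given in addition to schedule can offset missed prophylaxis doses. Full adherence without bleeds scores 1 to 2 points too high on a constant regimen and 2.6 points too high in the frequency-change example. For a subject on prophylaxis throughout, these errors are upward; for on-demand time the direction depends on where it falls.

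The interval count and the lost interval follow from the text alone. The bleed component rests on three assumptions: 1–3 infusions per bleed, all additional to schedule, and ABR within the range of the earlier pediatric study. It would vanish if unseen documents already restrict the numerator. The reach is the descriptive compliance summary and its 80% split.

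**What to change.** In SAP section 2, replace the compliance formulas with:

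Compliance % = 100 × P / (Σ dᵢ × fᵢ / 7 + 1)

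P is the number of infusions recorded as prophylaxis, from the first Treatment Phase prophylaxis dose to the last prophylaxis dose. The sum runs over contiguous regimen periods between those same two dates, split at the date of each regimen change, with dᵢ the days and fᵢ the prescribed infusions per week. Full adherence then gives 100% to within about 0.3 points on calendar dates.

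Two additions are best left out. An adjustment for bleed infusions that replace a scheduled dose would need information that the documents do not show to be collected. Ending the window at a switch to on-demand treatment would sit badly with reporting over the whole study in SAP 10.8.1.

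The cost is a change of SAP wording and a small programming edit. Prophylaxis doses must already be identified for the ABR window (SAP 10.7.1), and bleed infusions for the number per episode (SAP 10.7.2). Reported compliance may come out slightly lower. If the eCRF or shells already restrict the count, that part of the change only brings the SAP into line with them.
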